### 13. PHARMACOKINETIC ANALYSES

There are no PK, pharmacodynamics, or other assessments in this trial.

### 14. EXTENT OF EXPOSURE

Study treatment exposure will be summarized for each treatment group using the total number of doses taken and the duration of treatment.

Duration of study treatment will be calculated as follows:

- Duration of study treatment administration (days) = date/time of last administration – date/time of first administration

Study treatment compliance will be calculated as follows:

- Compliance (%): (actual number of used tablets in total) / (number of prescribed tablets to be taken) × 100
- Actual number of used tablets: number of tablets dispensed – number of tablets returned
- Prescribed number of tablets to be taken: duration of study treatment administration (days) × number of daily tablets

Study treatment compliance will be summarized by treatment group using counts and percentages as categorized below:

- >100%
- >90% to 100%
- >80% to 90%
- >70% to 80%
- ≤70%

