### Before Dosing:

- Review inclusion and exclusion criteria (Visit 3 only).
- Collect vital signs (blood pressure, heart rate, respiratory rate, temperature, and oxygen saturation).
- Record changes in concomitant medications.
- Symptomatic physical examination may be performed, if deemed necessary (e.g., to record any changes since screening or due to an AE). This may require an additional visit to the investigative site.

CONFIDENTIAL Page 32 of 68

- Record standard 12-lead ECG.
- Collect blood sample for routine laboratory testing (biochemistry and hematology).
- Collect urine sample for urinalysis and urine/creatinine ratio.
- Perform urine pregnancy test (women of childbearing potential).
- Perform urine drug screen.
- Perform SARS-CoV-2 test (Day 1 of Treatment Period 2 only).
- Record cough severity VAS.
- Complete LCQ.
- Complete CQLQ.
- Record any AEs since the last visit.
- The cough recorder will be disconnected 24 hours after fitting and retained by the investigative site.
- The first dose of trial treatment will be dispensed, and subjects will take the first dose (this must be after the completion of the cough monitoring).
- Visit 7 only: Unused trial medication and empty containers from Treatment Period 1 will be returned.

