## After Dosing:

- Collect vital signs (blood pressure, heart rate, respiratory rate, temperature, oxygen saturation) and record 2 hours (±30 minutes) after dosing.
- Dispense trial treatment to take home.

The subject will take the second dose of trial treatment at home before bedtime and will continue to take the randomized treatment twice daily for 14 days.

#### 5.2.2.5 Treatment Period Procedures - Visits 4 and 8

This visit may be conducted at the clinic or at another location such as the subject's home, according to the preference of the subject.

The following assessments and procedures will be performed:

- Collect vital signs (blood pressure, heart rate, respiratory rate, temperature, and oxygen saturation).
- Record changes in concomitant medications.
- Symptomatic physical examination may be performed, if deemed necessary (e.g., to record any changes since screening or due to an AE). This may require an additional visit to the investigative site.
- Record any AEs since the last visit.

CONFIDENTIAL Page 33 of 68

Subjects should be fitted with a cough recorder by 10:00 am. The cough recorder must be worn for 24 hours between fitting and disconnection. The subject will take the trial treatment at home before bedtime and will continue to take the randomized treatment twice daily.

## 5.2.2.6 Treatment Period Procedures - Visits 5 and 9

The following assessments and procedures will be performed:

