## After Dosing:

• Collect vital signs (blood pressure, heart rate, respiratory rate, temperature, oxygen saturation) and record at 2 hours (±30 minutes) after dosing.

Subjects will be instructed to take the last dose of trial treatment in the evening at the usual time.

## 5.2.2.7 End-of-Trial visit - Visit 10

The following assessments and procedures will be performed at the clinic:

- Collect vital signs (blood pressure, heart rate, respiratory rate, temperature, and oxygen saturation).
- Record changes in concomitant medications.
- Conduct physical examination, including review of the major body systems.
- Record standard 12-lead ECG.
- Collect blood sample for routine laboratory testing (biochemistry and hematology).

CONFIDENTIAL Page 34 of 68

- Collect urine sample for urinalysis and urine/creatinine ratio.
- Record any AEs since the last visit.
- Unused trial medication and empty containers from Treatment Period 2 will be collected or returned.

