7.4 Selection of Doses and Timing of Dose for Each Subject

## 7.5 Packaging and Labeling

The Sponsor will be responsible for ensuring that ADX-629 and placebo tablets are manufactured in accordance with applicable current Good Manufacturing Practice regulations and requirements.

CONFIDENTIAL Page 42 of 68

ADX-629 tablets or placebo will be provided in treatment kits for each period between trial visits. Each of the product bottles is capped with a child-resistant closure liner with an induction seal.

The IP will be administered as 300 mg tablets, i.e., one tablet BID for 14 days. BID dosing means every  $12 (\pm 1)$  hours. Each container will hold sufficient tablets to cover the time until the next scheduled visit, plus overage in case the scheduled visit is delayed.

The IP will be labeled according to the requirements of local law and legislation.

Further details regarding packaging, labeling and accountability are provided in the pharmacy manual.

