### 15.3 Vital Signs

Vital signs data will be collected on each study visit, including pre-dose and 2 hours ( $\pm 30$  minutes) post-morning dose on Day 1 and Day 14 of each treatment period. The following vital signs will be collected:

- Systolic blood pressure (mmHg)
- Diastolic blood pressure (mmHg)
- Respiration rate (beats/min)
- Pulse oximetry (%)
- Heart Rate (bpm)
- Temperature (C)

Vital signs will be summarized by treatment group using descriptive statistics at period baseline and at each post-baseline time point in the treatment periods. Changes from baseline will also be summarized. Here baseline is defined as the pre-dose value on the first day of administration for each period.

Additionally, vital signs will be summarized overall, using descriptive statistics at study baseline and End of Trial, including change from baseline. Here, baseline is defined as the last non-missing measurement (scheduled, unscheduled, or repeat) collected before the first administration of study treatment in the study.

Vital sign data will be listed for all subjects in the Safety population.

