## Standard Calculations

Variables requiring calculation will be derived using the following formulas:

- **Body Mass Index (BMI):** BMI is calculated using height and weight using and is calculated using the following formula:  $BMI (kg/m^2) = weight (kg) / [height (cm) / 100]^2$
- **Change from baseline:** Change from baseline will be calculated using the following formula:  $change = postbaseline\ value - baseline\ value$
- **Percent change from baseline:** Percent change from baseline will be calculated using the following formula:  $percent\ change\ from\ baseline = (postbaseline\ value - baseline\ value) / baseline\ value \times 100$ .
- **Study day:** For a given date, the study day will be calculated as the number of days from the day of first dosing of study treatment, labeled day 1, therefore:

Study day = date of event/measurement - date of first dose of study treatment + 1, for events/measurements on or after first dose

Study day = date of event/measurement - date of first dose of study treatment, for events/measurements before first dose

- **Durations (days):** Durations, expressed in days, will be calculated as follows:

Duration in days = (Stop date/time of event – Start date/time of event)/(3660x24)

If the stop or start time is missing, only the date information will be used as follows:

[figure not shown]
Duration in days = Stop date of event – Start date of event + 1

- **Height:** Height entries made in inches will be converted to centimeters using the following formula:

Height (cm) = Height (in) × 2.54

- **Weight:** Weight entries made in pounds will be converted to kilograms using the following formula:

Weight (kg) = Weight (lb)/2.2046

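### SAP 14 counts one dosing interval too few, so a subject who takes all 28 tablets scores about 103.7% compliance and is tabulated as over 100%

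*SAP*

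**What the plan says.** SAP section 14 builds compliance in three steps:

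- Duration of treatment, in days, is "date/time of last administration – date/time of first administration".
- The denominator is given as "Prescribed number of tablets to be taken: duration of study treatment administration (days) × number of daily tablets".
- Compliance is tablets used (dispensed minus returned) divided by that denominator, times 100. It is tabulated by treatment group as >100%, >90% to 100%, >80% to 90%, >70% to 80% and ≤70%.

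The dosing schedule is in the protocol:

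- Section 7.5: "The IP will be administered as 300 mg tablets, i.e., one tablet BID for 14 days", with doses every 12 (±1) hours.
- Section 5.2.2.4 (Visits 3 and 7): the first dose follows removal of the cough recorder on Day 1 and the second is taken at bedtime that day. The subject "will continue to take the randomized treatment twice daily for 14 days". SAP 15.3 confirms a morning dose on both days when it times vital signs "post-morning dose on Day 1 and Day 14 of each treatment period".
- Section 5.2.2.6 (Visits 5 and 9, Day 14): "Subjects will be instructed to take the last dose of trial treatment in the evening at the usual time".

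SAP Appendix A (Standard Calculations) has two general duration rules, neither of which section 14 cites. With times recorded, the difference is divided by 3660x24. With a time missing, the difference in dates is taken and one day is added.

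**The concern.** A first-to-last difference measures the gaps between doses, and there is always one gap fewer than there are doses. Multiplying that span by two tablets a day leaves one tablet out of the prescribed count. Section 14 adds back neither a closing dosing interval nor a day.

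The >100% row should show over-use. Under this formula it also collects fully adherent subjects, so it cannot be interpreted. Some subjects with missed doses appear one category too high. Protocol 7.8 defines severe non-compliance as below 80% or above 120% of correct dosing, so a reader will naturally set the table beside those limits, and the two would not be on the same scale. A subject with a single dose is in the Safety Population but has no computable compliance.

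**Working it through.** The documents give no compliance figure to reproduce, so this applies the section 14 formula to the protocol schedule.

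**Inputs**
- Tablets per full period: 1 × 2 × 14 = 28 (protocol 7.5).
- First dose Day 1 morning; last dose Day 14 evening (protocol 5.2.2.4 and 5.2.2.6, SAP 15.3).
- Interval 12 (±1) hours (protocol 7.5).
- Assumed: duration is computed per treatment period, and all unused tablets are returned.

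**Full course, dose times recorded**
- Span: 27 intervals × 12 h / 24 = 13.5 days.
- Prescribed tablets: 13.5 × 2 = 27.
- Compliance: 28 / 27 = 103.7%, in the >100% row.
- Last interval 13 h: 28 / (2 × 13.542) = 103.4%. Last interval 11 h: 28 / (2 × 13.458) = 104.0%.
- Assumed clock times, 08:00 to 24:00: 28 / (2 × 13.667) = 102.4%. 11:00 to 18:00: 28 / (2 × 13.292) = 105.3%.
- Protocol 7.1 allows 14 (±2) days per period. At 12 days, 24 / 23 = 104.3%; at 16 days, 32 / 31 = 103.2%.

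**Missed doses between on-schedule first and last doses**

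| Tablets used | % of 28 | SAP 14 % (last interval 13, 12, 11 h) | Category |
|---|---|---|---|
| 27 | 96.4 | 99.7, 100.0, 100.3 | up one only if under 12 h |
| 25 | 89.3 | 92.3, 92.6, 92.9 | up one |
| 24 | 85.7 | 88.6, 88.9, 89.2 | unchanged |
| 22 | 78.6 | 81.2, 81.5, 81.7 | up one |
| 21 | 75.0 | 77.5, 77.8, 78.0 | unchanged |
| 19 | 67.9 | 70.2, 70.4, 70.6 | up one |

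**Adherent subjects who stop early**

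| Last dose | Tablets taken | SAP 14 |
|---|---|---|
| Day 7 evening | 14 | 14 / (2 × 6.5) = 107.7% |
| Day 7 morning | 13 | 13 / (2 × 6) = 108.3% |
| Day 2 evening | 4 | 4 / (2 × 1.5) = 133.3% |
| First dose only | 1 | 1 / 0, undefined |

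**If a dose time is missing (full course)**
- Section 14 subtraction on dates alone: 13 × 2 = 26; 28 / 26 = 107.7%.
- Appendix A rule with the added day: 14 × 2 = 28; 28 / 28 = 100%.

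**Appendix A divisor**
The rule reads "Duration in days = (Stop date/time of event – Start date/time of event)/(3660x24" (closing bracket follows). A day has 3600 × 24 = 86,400 seconds; 3660 × 24 = 87,840. Only if a programmer applied this to treatment duration would it matter here: 86,400 / 87,840 = 0.9836, and 28 / (27 × 0.9836) = 105.4%.

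**The case against.** Four points can fairly be made against this.

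**It is only a descriptive table.** No hypothesis test uses it, and both treatments share the formula. The protocol's 80%/120% limits are applied by the investigator from tablet counts (protocol 7.8) without reference to SAP 14. Total doses taken is also summarised. All of this stands, and it limits the importance of the point. It does not make the table correct.

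**The final dose time may not be recorded.** The last dose is taken in the evening after the Day 14 visit, and the protocol describes no dosing diary. With the Appendix A date-only rule the full course scores 100%. That is possible, but section 14 specifies date/time and does not cite that rule. If the rule is used only where a time is missing, two subjects with identical dosing land in different rows.

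**The category shifts depend on clock times.** This is true outside the 11- to 13-hour range. At 11:00 to 18:00, 24 tablets give 24 / 26.583 = 90.3% and do move up. At 08:00 to 24:00, 19 tablets give 19 / 27.333 = 69.5% and do not. The table of missed doses holds only for the range stated. The score for full adherence exceeds 100% at every combination examined.

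**The correction still ties the prescribed count to the last dose taken.** A subject who omits only the final evening tablet takes 27 over 13 days. The corrected count is round(26) + 1 = 27, hence 100%, although 27 of 28 is 96.4%. This limit is real. It comes from the SAP's own choice of first-to-last dosing as the reference, and the current text does worse (27 / 26 = 103.8%).

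**Conclusion.** The concern holds. With dose times recorded, SAP 14 prescribes 27 tablets for a 28-tablet course and reports full adherence as 103.7%. Reported treatment duration is 13.5 days where protocol 5.4 describes 14. This is a stated rule that returns a wrong answer, not a missing detail.

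The result assumes duration computed per period, on-schedule first and last doses, and complete return of unused tablets. The excess is larger for early stoppers. The 3660x24 slip is a separate error that affects compliance only if that rule is applied to treatment duration.

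The consequence is limited to the duration and compliance summaries. It should be corrected before they are produced, but it does not bear on the efficacy conclusions.

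**What to change.** In SAP section 14:

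1. Define prescribed tablets as the number of scheduled twice-daily doses from first to last dose inclusive: round(2 × elapsed days) + 1. This gives 28, 14, 13, 4 and 1 for the full course and the four early stops above, so each adherent subject scores 100%. It also returns 28 for first doses at 08:00, 10:00 or 11:00 combined with last doses at 18:00, 20:00, 22:00 or 24:00. State that halves round up: a 12:00 to 18:00 course gives exactly 2 × 13.25 = 26.5.
2. Report treatment duration with the final interval included, as that count divided by 2 (14.0 days for the full course).
3. State one rule for a missing dose time that agrees with item 1, for example counting doses from the date and the morning or evening slot. Adding a day to the dates is not enough: an adherent subject stopping on the morning of Day 7 would score 13 / 14 = 92.9%.
4. Note that tablets omitted after the last dose taken are not captured by this measure.

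In Appendix A, correct 3660x24 to 3600x24.

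The cost is a few lines of SAP wording and the matching programming. No protocol change is needed.

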### 15. SAFETY ASSESSMENTS AND ANALYSES

All safety analyses will be based on the Safety population.

#### 15.1 Adverse Events

##### 15.1.1 Definition of Adverse Events

An AE is defined as any untoward medical occurrence in a clinical investigation subject administered a pharmaceutical product and which does not necessarily have a causal relationship to this treatment. An AE can therefore be any unfavorable and unintended sign (including an abnormal laboratory finding), symptom or disease temporally associated with the use of a medicinal (investigational) product, whether or not related to the treatment administered.

An SAE is defined as any untoward medical occurrence that at any dose:

- Results in death, or
- Is life-threatening, i.e., the subject was at immediate risk of death at the time of the event, or
- Requires in-patient hospitalization or prolongation of existing hospitalization, or
- Results in persistent or significant disability or incapacity, or
- Is a congenital anomaly/birth defect; or
- Is an important medical event, i.e., may not be immediately life-threatening or result in death or hospitalization but may jeopardize the subject or may require intervention to prevent one of the other outcomes listed above. Examples of such events are: bronchospasms requiring intensive treatment in an emergency room or at home, blood dyscrasias, or convulsions that do not result in hospitalization. Development of cancer, drug dependency, or drug abuse are most often considered as SAEs.

The following are not considered to be SAEs:

- Any elective procedures that require admission to hospital as well as any planned elective procedures (e.g., angioplasty) planned prior to signing the informed consent form, unless the underlying condition has worsened or the procedure results in a worsening of the subject's condition. Such conditions should be recorded in the subject's medical history.
- A visit to an emergency room or other hospital department for <24 hours that does not result in admission to hospital unless the reason is considered to be an important medical event or a life-threatening event. These should be recorded as AEs.

Severity of an AE is defined as a qualitative assessment of the degree of intensity of an AE as determined by the Investigator or reported by the subject. The assessment of severity is made irrespective of relationship to trial procedures or seriousness of the event and should be evaluated according to the following scale:

Assessment of causality is based on the following considerations: associative connections (time or place), pharmacological explanations, previous knowledge of the drug, presence of characteristic clinical or pathological phenomena, exclusion of other causes, or absence of alternative explanations.

The Investigator will assess the causal relationship to the trial treatment according to the following classifications:

- **Definite:** A clinical event, including laboratory test abnormality, occurring in a plausible time relationship to drug administration and which cannot be explained by concurrent disease or other drugs or chemicals. The response to withdrawal of the drug (de-challenge) should be clinically plausible. The event must be definitive pharmacologically or phenomenologically using a satisfactory re-challenge (the drug is readministered to determine if the same reaction occurs) procedure if necessary.
- **Probable:** A clinical event, including laboratory test abnormality, occurring in a plausible time relationship to drug administration and which cannot be explained by concurrent disease or other drugs or chemicals. The response to withdrawal of the drug (de-challenge) should be clinically plausible.
- **Possible:** A clinical event, including laboratory test abnormality, with a reasonable time sequence to the drug administration, but which could also be explained by concurrent disease or other drugs or chemicals. Information on drug withdrawal may be lacking or unclear.
- **Unlikely (“Not related”):** A clinical event, including laboratory test abnormality, with a temporal relationship to drug administration which makes a causal relationship improbable and in which other drugs, chemicals or underlying disease provide plausible explanations.
- **Not related:** Any event that does not meet the above criteria; there is sufficient information that etiology of the event is in no relation to the trial treatment.

### 15.1.2 Adverse Event Analyses

All AE summaries will be restricted to treatment-emergent AEs (TEAEs), defined as those AEs that occurred after the first dose of trial drug or existing AEs that worsened during the study after the first dose administration. If it cannot be determined whether the AE is treatment-emergent because of a partial-onset date, it will be considered treatment-emergent. Verbatim terms in the eCRFs will be mapped to PTs and SOCs using the MedDRA. The version of MedDRA used will be specified in the final Medical Coding Plan.

AEs reported with relationship to study treatment of “Definite,” “Probable,” and “Possible” will be considered related AEs and “Unlikely” and “Not Related” as not related AEs for all relationship-to-study-treatment summaries.

In situations with missing data, the worst-case will be applied; that is, seriousness will be assigned as “Yes” if seriousness is missing, the severity will be assigned as “Severe” if the severity is missing, and relationship to study treatment will be assigned as “Related”.

The following rules will be used to assign a TEAE to a treatment:

- A TEAE will be assigned to the treatment received immediately before onset.

- Any TEAE reported within the washout period between doses will be attributed to the previous treatment received.

Each AE summary will be displayed by treatment group. Summaries displayed by SOC and PT will be ordered by descending order of incidence of SOC and PT within each system organ class. Summaries will display the number and percentage of subjects with at least 1 event by treatment group.

Summaries of the following types will be presented:

- Overall summary of TEAEs that contains an overview of each item below
- Subject incidence of TEAEs and the total number of unique TEAEs by MedDRA SOC and PT.
- Subject incidence and the total number of unique events of Related TEAEs by MedDRA SOC and PT.
- Subject incidence and the total number of unique events of Serious TEAEs by MedDRA SOC and PT
- Subject incidence and the total number of unique events of Serious Related TEAEs by MedDRA SOC and PT
- Subject incidence of TEAEs by MedDRA SOC, PT, and highest severity. At each level of subject summarization, a subject is classified according to the highest severity if the subject reported 1 or more events.

AEs will be listed for all subjects in the Safety population.

Separate listings of AEs leading to death, serious AEs (SAEs), and AEs leading to permanent treatment discontinuation will be provided.

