## 4.2 Endpoints

# 4.2.1 Primary Endpoints

The primary endpoints of this trial are:

- Incidence and severity of TEAEs and serious adverse events (SAEs)
- Observed values and changes from baseline of:
  - Laboratory safety parameters
  - Vital signs
  - 12-lead electrocardiogram (ECG) parameters

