- Complete CQLQ.
- Record any pre-treatment AEs with onset after the subject has signed the ICF.

CONFIDENTIAL Page 31 of 68

• Subjects will be fitted with a cough recorder by 10:00 am, which must be worn for 24 hours of recording time. The cough recorder may be returned to the investigative site by courier after the 24-hour recording.

Subjects who fulfill the trial eligibility criteria will be given appointments for their participation in the trial.

If a subject visit falls outside the screening period window or repeat assessments are required, screening may be extended with approval from the Medical Monitor. If extended beyond 21 days, some of the screening procedures and assessments may need to be repeated.

Subjects who have screen failed may be re-screened once if their eligibility characteristics have changed. Subjects who are re-screened must be assigned a new subject number. The re-screening process for such subjects must be discussed with the Medical Monitor.

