## 8.3.1.2 Adverse Event Reporting

[figure not shown]
Adverse events will be collected with a non-leading question at each visit: "Have you experienced any change in your health or in your general condition since your last visit?" as well as by reporting those events directly observed and spontaneously reported by the subject. Clearly related signs, symptoms, and abnormal diagnostic procedures should preferably be grouped together and recorded as a single diagnosis or syndrome whenever possible. Intensity (mild, moderate, or severe) and relationship to trial treatment (related or unrelated) as well as action taken, seriousness and outcome should be recorded in the AE page of eCRF. Start and end date and time of the event will also be recorded as precisely as possible.

Abnormal laboratory values or vital signs abnormalities are to be recorded as AEs only if they are medically relevant, i.e., symptomatic, requiring corrective treatment, leading to discontinuation or fulfill a criterion for an SAE.

In the case of chronic disease, if the disease is known and documented when the subject enters the trial, only worsening (increased frequency or intensity of the episodes) will be documented as an AE.

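### SAP 15.1.2 counts worsened adverse events as treatment-emergent but assigns them by onset alone, so some worsening is not counted under the treatment on which it occurred

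*SAP*

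**What the plan says.** SAP 15.1.2 restricts all adverse event summaries to TEAEs. Its definition has two limbs: "those AEs that occurred after the first dose of trial drug or existing AEs that worsened during the study after the first dose administration". Both limbs are measured from the first dose in the study, not the first dose of each period.

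Two rules place a TEAE in a treatment column. The general rule is "A TEAE will be assigned to the treatment received immediately before onset". The washout rule is "Any TEAE reported within the washout period between doses will be attributed to the previous treatment received". Neither mentions worsening. Every summary is shown by treatment group, and in the severity table "a subject is classified according to the highest severity if the subject reported 1 or more events".

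On recording, the screening visit in Protocol 5.2.2.1 includes the instruction "Record any pre-treatment AEs with onset after the subject has signed the ICF". Protocol 8.3.1.2 asks for intensity and for start and end dates and times, and names no date of worsening. It addresses worsening once: for chronic disease already documented at entry, "only worsening (increased frequency or intensity of the episodes) will be documented as an AE".

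**The concern.** The definition has a worsening limb and the allocation rules do not. A worsened event therefore has to be placed by a rule written for new events. In a crossover that matters, because the subject may have been on the other treatment, or on none, when the event first appeared.

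Incidence and severity of TEAEs is the first primary endpoint (Protocol 4.2.1, SAP 3.3), and the by-treatment tables are its planned summary. If a treatment aggravates events that are already present, those tables are where it should show. Under the rule as written, some of that aggravation would appear in the other treatment's column or in no column.

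**Working it through.** The plan states no figure to reproduce here. The check traces the rules case by case and then works out the scale.

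**What onset means.** SAP 15.1.2 does not define onset for a worsened event. SAP Appendix A, on missing or incomplete dates, refers to the onset date of an adverse event and then resolves it with algorithms for start and stop dates. The SAP's own usage therefore treats onset as the recorded start.

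**Case trace.** Assumptions: onset is the recorded start, there is one record per event, and the record carries the highest intensity reached. S1 is ADX-629 then placebo; S2 is placebo then ADX-629.

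| Case | Column under the current rules |
|---|---|
| New event within a period | That period's treatment; the rule works |
| Starts in Period 1, worsens in Period 2 | Period 1 treatment only, at the worsened severity |
| Starts in the washout, worsens in Period 2 | Period 1 treatment only, at the worsened severity |
| Starts after consent and before the first dose, then worsens on treatment | A TEAE, but no treatment precedes its onset, so none is returned |
| Chronic disease known at entry worsens | The worsening is itself the event, so it is placed normally |
| Any worsening entered as a new record with its own start date | Placed normally |

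In the second and third cases the initial event belongs under the Period 1 treatment. What is misplaced is the worsening and its severity. In S2, worsening on ADX-629 is shown under placebo; in S1, worsening on placebo is shown under ADX-629. Because emergence is measured from the first dose in the study, a Period 2 worsening does not qualify as a fresh event.

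**Comparison with the rest of the SAP.** SAP 11.5 assigns a medication taken in both periods to both treatments. SAP 15.2, 15.3 and 15.5 measure laboratory, vital sign and ECG changes by treatment from the pre-dose value of each period. Adverse events have neither provision.

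**Scale.** Assume about 50 subjects contribute to each treatment column (SAP 5 gives approximately 50 randomized; every subject is planned to receive both treatments).

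- One subject in one column: 1/50 = 2 percentage points.
- Overall incidence, for an event that starts mild on placebo and becomes severe on ADX-629: counting the worsening adds 1/50 to ADX-629 and leaves placebo unchanged. The difference moves by 2 points, or by 0 if that subject already has another ADX-629 TEAE.
- Severe row, same event: placebo loses 1/50 and ADX-629 gains 1/50. The difference moves by 2 + 2 = 4 points, provided the subject has no other severe event in either column.
- Pre-dose event that worsens: it enters one column where there was none, so the overall incidence difference moves by at most 2 points.

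The number of such events cannot be derived. The documents' only observed TEAE rates are the Phase 1 figures in Protocol 3.2, 9.4% on ADX-629 and 19.1% on placebo in healthy volunteers. They do not show how many events persist across a washout or worsen.

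**The case against.** The strongest reply is that the SAP says onset, not original onset. A pre-dose event becomes a TEAE only when it worsens, so the onset of that TEAE could be taken as the worsening, and then it has a treatment. That reading is possible and would also resolve the Period 2 cases. But the SAP does not state it, Appendix A points the other way, and no date of worsening is named for collection. A programmer would have to choose.

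Second, if sites open a new record when an event worsens, every problem case disappears. This stands. The eCRF and its completion rules are not among the documents, so actual practice is unknown. Neither document requires a new record, except that worsening of chronic disease known at entry is itself recorded as the event. That exception does not cover events arising between consent and first dose, or events arising in Period 1.

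Third, all adverse events are listed, with separate listings for serious events, deaths and permanent discontinuations, and no hypothesis test on adverse events is planned. This limits the harm. But a listing with one start date and one intensity per event may not show when the worsening occurred.

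A reader might infer that the rule systematically favours ADX-629, or that the whole event is charged to the wrong treatment. The documents support neither. Misplacement runs in both sequences, and spontaneous worsening would tend to balance between them. An event that began on placebo is properly a placebo event, whatever happens later.

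**Conclusion.** The gap is real and should be closed before unblinding. Read literally, SAP 15.1.2 leaves a worsened post-consent, pre-dose event without a treatment. It also shows the Period 2 worsening of an earlier event, at the higher severity, under the Period 1 treatment only.

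This rests on two readings: onset is the recorded start date, and worsening stays on the same record. The first follows the SAP's own usage; the second is left open by the documents.

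The scale is the per-subject shift shown above. No total shift can be stated. The net direction depends on the true effect: if ADX-629 aggravates existing events, the difference between treatments is understated.

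**What to change.** In SAP 15.1.2:

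- Assign a worsened event to the treatment most recently taken before the date of worsening.
- Assess emergence and worsening against the first dose of each period.
- Count an event that starts in Period 1 or the washout and worsens after the first Period 2 dose twice: under the Period 1 treatment at its initial severity, and under the Period 2 treatment at its worsened severity. This matches the SAP 11.5 rule for medications that span both periods.

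In data collection, have sites enter worsening as a new adverse event line with its own start date. Where that is no longer practical, query worsening dates before database lock.

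The cost is a few sentences in the SAP and one recording instruction or round of queries. Protocol section 10 has the SAP finalized before lock and unblinding, so the change belongs there; under SAP section 8, an analysis performed after the blind is broken would be post hoc. The downside is small: such events appear in both columns, which a footnote can state. Other conventions are possible, but one must be fixed in advance.
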